### 16.3 Safety Analyses

All treated subjects will be considered evaluable for safety. Safety assessments will be based on Adverse Events. A listing of all Adverse Events and related variables will be presented. If a sufficiently large number of Adverse Events are observed, then summary tables will present incidence rates in terms of treatment configuration for all subjects who enter the treatment period.

The skin reactions (erythema, edema, rash, and dryness; see Section 15.2, Skin Irritation Scoring System) of the test product, positive control, and negative control will be evaluated at baseline sampling and post-product application, and will be tabulated in the final report.

The statistical significance of differences in skin irritation between the three treatments will be evaluated using Fisher's exact test on skin irritation data summarized as follows: any reaction above zero (no reaction) on the skin irritation rating scale for any category (erythema, edema, rash, and dryness) will be considered a positive signal for that substance. If Fisher's exact test shows statistically significant skin irritation between the three treatments, a secondary analysis will be conducted to determine how the reactions differ.

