#### Treatment Balance

Each subject will receive two different treatments, one on the right side of the body and one on the left.

[figure not shown]
The treatment assignments will be balanced such that the number of readings per anatomical site matches the calculated requirements.

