## 15.2 Evaluation of Skin Reactions

The skin at each site will be evaluated visually for irritation per a scoring matrix (below) immediately before screening-baseline, baseline, and post-treatment samples are taken from each site. A subject will be dismissed from the study if skin irritation scores of 1 are observed on the test sites prior to screening-baseline or treatment day baseline sampling.

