#### **16.2 Efficacy (Primary) Analyses**

CFU values will be calculated as per Section 13.9. Individual plate CFU counts that are zero will be treated as 0.5 for further calculations. Changes from baseline will be calculated separately for each subject and for each of the three non-baseline sites by taking the baseline  $\log_{10}$  CFU/cm^2 values and then subtracting the  $\log_{10}$  CFU/cm^2 values for the samples taken after the baseline. Therefore, a subject who completes all treatments and passes all baseline requirements will have 4 (sites) \* 3 (post-application samples per site) = 12 changes from baseline reported. Responder status will be calculated for each reported  $\log_{10}$  CFU/cm^2 reduction. The sites will be considered responders based on the sample time and body area:

For the groin at 30 seconds or 10 minutes, a  $\log_{10}$  CFU/cm^2 reduction  $\geq 3.0$  is considered a responder.

For the abdomen at 30 seconds or 10 minutes, a  $\log_{10}$  CFU/cm^2 reduction  $\geq 2.0$  is considered a responder.

For either the groin or the abdomen at 6 hours, a  $\log_{10}$  CFU/cm^2 value less than baseline (i.e., a  $\log_{10}$  CFU/cm^2 reduction  $> 0$ ) is considered a responder.

Responder statuses will be grouped by body area, sample time, and test substance. Exact confidence intervals will be calculated for responder rates. The primary efficacy goal is to have the 95% confidence intervals for the responder rate at 10 minutes to be  $\geq 70\%$ . The secondary efficacy goals are to have the 30-second and 6-hour 95% confidence intervals for the responder rates to be  $\geq 70\%$ .

Differences in responder rates between treatments and their confidence intervals will be calculated using asymptotic (approximate) methods. If differences in responder rates are not reliable based on approximate methods, which happens when rates are near either 100% or 0%,  $\log_{10}$  CFU/cm^2 confidence intervals for the differences will be used for comparison instead.

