Two-sided confidence intervals for  $\log_{10}$  CFU/cm^2 changes from baseline will also be calculated. These calculations will use an ANOVA model with subject as a random variable and test substance as a fixed variable. Body area (abdomen or groin) will be a fixed variable. Sample times (30 seconds, 10 minutes, or 6 hours) will be calculated separately using identical models. Differences in  $\log_{10}$  CFU/cm^2 reductions will be calculated based on the same model.

Any deviation(s) from the statistical analysis plan will be described and justified in the final report.

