### CHANGE(S):

In Section 13.3 on Page 19 of the Protocol, for the Left/Right Balance, the statement "The application will be randomized so that each treatment is used on an equal number of left and right sides of the body with the exception of replacement subjects." will be changed to, "The application will be randomized so that each treatment is used on an equal number of left and right sides of the body."

On page 2 of Appendix 1, the procedure for ZuraPrep™ Vehicle (Negative Control) [REDACTED]

[REDACTED] This will be changed to: [REDACTED]

In Section 15.4 (Anticipated Reactions), Page 27 of the Protocol, and on Page 8 of the Informed Consent Form as well as Page 7 of the Informed Consent Form - Neutralization Assay, in the Risks sections, folliculitis will be added as an anticipated reaction from clipping. For the Informed Consent Form, and new version of the Form will be created (Version 02) and approved by the GIRB. Clipping has already occurred for the neutralization, therefore, a subject letter will be signed by subjects who clipped in the neutralization – the letter will be approved by the GIRB. See attached letter for neutralization subjects, and version 02 of the Informed Consent Form.

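### The Fisher's exact test on skin irritation (Section 16.3) ignores that each subject carries two or three treatments, so its error rate is not the nominal one; the consequence is minor

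*Combined protocol and SAP*

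**What the plan says.** Section 16.3 names a single inferential safety test: "The statistical significance of differences in skin irritation between the three treatments will be evaluated using Fisher's exact test". Scores are first reduced to yes or no. Any score above zero in any of the four skin categories "will be considered a positive signal for that substance". A follow-up analysis of how the reactions differ is run only if this test is significant, and its method is not named. Section 16.3 gives no alpha, does not define the row of the table, and does not say how body areas and time points are combined.

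The design is paired within subject. Section 13.3 (Treatment Balance) reads: "Each subject will receive two different treatments, one on the right side of the body and one on the left". The amendment of 04/06/2017 replaces that sentence. It assigns two treatments per anatomical site and allows up to three per subject when both areas qualify.

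Scores exist by site. Section 15.2 says: "The skin at each site will be evaluated visually for irritation per a scoring matrix", and it does so before each sample. For the log10 reductions, Section 16.2 does model the subject: "These calculations will use an ANOVA model with subject as a random variable and test substance as a fixed variable". Section 16.3 has no counterpart.

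**The concern.** Fisher's exact test gets its p-value by treating every row as a separate, independent unit. Here almost every subject supplies at least two rows, and those rows sit under different treatments. Skin that reddens easily on one side will plausibly do so on the other, and the test cannot see this.

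The plan would then report a p-value whose error rate is unknown. If the test is conservative, a real irritation difference between the test product and ChloraPrep is more likely to be missed, and the follow-up analysis then does not run. If it is anti-conservative, a difference may be reported that is not there.

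**Working it through.** **Inputs from the documents (Sections 7.0 and 11.1).** Subjects: 288 ZuraPrep/ChloraPrep, 32 ZuraPrep/vehicle and 32 ChloraPrep/vehicle. These reproduce the plan's counts:
- 288 + 32 + 32 = 352 subjects
- 2 × 352 = 704 evaluations per body area
- 288 + 32 = 320 per active
- 32 + 32 = 64 for vehicle

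**Assumed, because the documents do not give them:** irritation rates, within-subject correlation and a two-sided alpha of 0.05.

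**Step 1: direction, one row per subject and substance, original allocation.** The table has 320/320/64 rows. Let q be the binary variance and r the correlation between a subject's two rows.
- ZuraPrep minus ChloraPrep: the naive variance is 2q/320. The 288 shared subjects remove 2rq × 288/320². The ratio of true to naive variance is 1 − 0.9r.
- Vehicle minus an active: the naive variance is q(1/64 + 1/320) = 6q/320. The 32 shared subjects remove 2rq × 32/(64 × 320) = rq/320. The ratio is 1 − r/6.

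| r | ZuraPrep v ChloraPrep | Vehicle v active |
|---|---|---|
| 0.2 | 0.82 | 0.97 |
| 0.5 | 0.55 | 0.92 |
| 0.8 | 0.28 | 0.87 |

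Fisher's test works with too large a variance. The excess is large between the actives and small for vehicle contrasts.

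**Step 2: type I error.** Site outcomes were simulated from a latent normal with the same correlation among a subject's four sites. A row is positive if either site on that side is positive. The exact three-group (Freeman-Halton) p-value was used. The latent correlation below is on a different scale from r in Step 1.

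| Latent correlation | Type I error at nominal 0.05 |
|---|---|
| 0 | near nominal |
| 0.3 | about 0.035–0.045 |
| 0.6 | about 0.03 (0.015–0.030 over site rates of 2–20%) |
| 0.9 | about 0.01 |

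**Step 3: power on the same rows, Fisher against a paired test.** Site rates are in the order ZuraPrep/ChloraPrep/vehicle.
- 20/14/14%: about 67 v 77% at correlation 0.3, and 58 v 84% at 0.6.
- 14/14/24% at 0.3: 57 v 63%.
- 20/20/10% at 0.3: 66 v 69%.

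For vehicle-only differences, the loss due to pairing at 0.3 is therefore about 2 to 6 points. The paired figures move by a few points with the form of the paired test.

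**Step 4: other rows.** With one row per site and time point, and readings correlated within a site, the level was 0.16–0.29 (Pearson chi-square in place of Fisher). With one row per site it was about 0.04–0.07.

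**Step 5: after the amendment.** Suppose abdomen and groin pairs were drawn independently in the 288:32:32 ratio. This is an assumption: the amendment says only that up to three treatments are possible. An active falls on a given area with probability 320/352 = 0.909, and vehicle with 64/352 = 0.182. Sites per row are then:
- active: 2(0.909)/(1 − 0.091²) = 1.83
- vehicle: 2(0.182)/(1 − 0.818²) = 1.10

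Under the original allocation both are 2. If half of the subjects were paired this way, the figures are 1.91 and 1.42; if a quarter, 1.96 and 1.66. An active row then has more chances of any reaction than a vehicle row. At site rates of 10–20% and correlation 0.3–0.6, the type I error is 0.029–0.060 for a quarter of subjects and 0.043–0.170 for half. This comes from unequal exposure, which is a different fault from dependence.

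**The case against.** The strongest case against is that little depends on this p-value. Section 16.3 bases safety assessment on adverse events, and skin reactions are tabulated whatever the test shows. A score of 3 counts as an adverse event and leads to discontinuation under Sections 15.2 and 12.0 without any test. All of this stands, and it is why the point is minor.

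It can also be said that nothing is lost if a subject's two sides are uncorrelated. That is right. If mainly same-side sites are alike (0.6–0.9, with 0–0.3 across sides), the simulated level was 0.035–0.056. Correlation between sides is plausible, but the documents give no figure.

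Three stronger readings are tempting and are not supported:
- **The test is conservative throughout.** This needs the subject-and-substance row, which the wording on a signal for a substance suggests but does not state. It also needs the original allocation, which the amendment of 04/06/2017 replaced for later subjects.
- **The amendment seriously inflates false positives.** If all subjects were paired separately the simulated level reaches 0.145–0.471. However, the 03/30/2017 amendment that led to this change was made during recruitment, so not all subjects can fall under it. The share is not given and independent draws are an assumption.
- **Pairing alone costs very large amounts of power.** Comparing Fisher's test with a paired analysis of site-level outcomes mixes two changes. For 14/14/24% at correlation 0.3, the figures are Fisher 57%, paired on the same rows 63%, and paired at site level 70%. More than half of that gap comes from changing the outcome.

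**Conclusion.** The point holds, as a minor one. The stated test assumes independence that the design does not provide, and this is a wrong rule rather than a missing detail. On subject-and-substance rows under the original allocation, with positive correlation between sides, the test is conservative. The power loss falls mainly on ZuraPrep against ChloraPrep: about 10 points at latent correlation 0.3 and 26 at 0.6 in the 20/14/14% example. Vehicle contrasts lose little.

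The direction cannot be stated without those conditions. Site-by-time rows would reverse it, and separate pairing of the two areas would make the any-reaction signal not comparable between substances. Every size given here rests on assumed irritation rates, correlations and alpha.

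**What to change.** In Section 16.3:
- Define the outcome as one record per treated site: any post-application score above 0 in any category. Each record then carries the same exposure, which also removes the unequal site count.
- Replace Fisher's test with one three-treatment (2 degrees of freedom) test that accounts for the subject, with body area as a factor, at two-sided 0.05. Either of two is sound: a score test from a subject-clustered logistic (GEE) model, or a permutation test that follows the allocation actually used. The second is preferable if irritation is expected to be rare. It needs the allocation schedule, including the side assignment: "The application will be randomized so that each treatment is used on an equal number of left and right sides of the body".
- Name one of the two before the skin data are analysed, and do not choose it on the observed irritation rate. Staff who apply product and take samples are not blinded (Section 13.8), so the order matters.
- Use pairwise contrasts from the same method as the follow-up.

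The amendment of 08/29/2017 was issued after testing was complete, so this has to be reported as a justified deviation. Section 16.2 provides the route: "Any deviation(s) from the statistical analysis plan will be described and justified in the final report".

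The cost is a little programming on site scores already collected, and a change from a per-substance to a per-site signal. If the two sides prove uncorrelated, little is gained.

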## **12.0 SUBJECT WITHDRAWAL AND DISCONTINUATION**

The Investigator (or Subinvestigators) may discontinue individual subjects from the study at any time. Subjects may voluntarily withdraw from the study at any time without reason or consequence. The subject will be asked to report the reason for withdrawal. The Investigator will provide a written report on the appropriate source document or Case Report Form (CRF) including the date and reason for discontinuance. Subjects who qualify on Screening Baseline Day and begin the treatment phase may not be re-entered into the study, regardless of whether or not they completed the study.

Any enrolled subject will be discontinued for the following reasons:

1. A skin irritation rating of 3 for any individual skin condition at any evaluation following the application of study treatment. (A skin irritation rating of 2 for any individual skin condition at any evaluation following the application of study material may also be the cause for subject discontinuation at the discretion of the Investigator).
2. Experiencing a serious protocol deviation that compromises the data results, for example, using a topical antibiotic at a test site during the study.

Reference Sections 13.3, 13.9 and 17.3 for handling of withdrawn subject data.

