#### **15.4 Anticipated Reactions**

The risks associated with this test are primarily related to application of a test material. Mild abrasion may occur due to cylinder sampling. Adhesive reactions are also possible. Mild skin irritation is anticipated and in some cases mild to heavy erythema, swelling, itching, cracking, peeling, or in rare cases, blistering and/or an allergic reaction might occur.

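### Section 16.3 ends the between-product comparison of skin irritation at a non-significant Fisher test, with no difference, no interval and no inference by grade

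*Combined protocol and SAP*

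**What the plan says.** Section 16.3 names the test: "The statistical significance of differences in skin irritation between the three treatments will be evaluated using Fisher's exact test". It defines the outcome as a yes/no result, in which "any reaction above zero (no reaction) on the skin irritation rating scale for any category" counts as positive. Scores of 1, 2 and 3 therefore count alike. Anything further is conditional: "If Fisher's exact test shows statistically significant skin irritation between the three treatments, a secondary analysis will be conducted to determine how the reactions differ". The follow-up method, the alpha and the unit (site, subject or time point) are not given.

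Some reporting does not depend on the test. Section 16.3 says the skin reactions "will be evaluated at baseline sampling and post-product application, and will be tabulated in the final report", and it lists all Adverse Events. Under Section 15.2 a score of 3 is an Adverse Event, and Section 15.3 ties each event to the material applied at that site. Incidence tables for Adverse Events are promised only if there are enough events. Section 12.0 takes a rating of 3 as a reason to discontinue, and treats the next grade down as a possible one: "A skin irritation rating of 2 for any individual skin condition at any evaluation following the application of study material may also be the cause". Section 15.4 sets expectations: "Mild abrasion may occur due to cylinder sampling. Adhesive reactions are also possible. Mild skin irritation is anticipated".

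Efficacy is handled differently. Section 16.2 plans treatment differences in responder rates with confidence intervals and attaches no significance condition. The amendment of 08/29/2017 adds interval-based comparisons with ChloraPrep and with vehicle.

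**The concern.** A non-significant p-value is compatible with no excess of irritation and also with a sizeable one. Only an estimate with an interval tells the two apart, and Section 16.3 plans neither, with the comparison between products going further only when the omnibus test rejects. Tables of scores by product give the counts, but no difference and no limit on the excess that the data allow.

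The yes/no signal adds a second weakness. A mild, transient 1 weighs the same as a 2, although the protocol itself treats a 2 as possibly serious enough for discontinuation. If mild reactions are common under every product, a shift in grade barely moves the signal. At stake is what the report can say about the irritancy of a new preparation relative to its comparator and its own vehicle.

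**Working it through.** **Inputs from the documents (Section 11.1).** The planned counts reproduce: 288 + 32 + 32 = 352 subjects; 352 × 2 sides = 704 sites per body area; 288 + 32 = 320 sites for each active; 32 + 32 = 64 for vehicle. These are size figures, not a power statement for irritation. The text of Section 7.4 is not visible in the public copy, so nothing is inferred from it.

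**Assumptions.** Irritation rates, because the documents give none; two-sided alpha 0.05, because none is stated for this test; one result per site.

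**Test.** With *t* positive sites in total, each 2×3 table has probability C(320, z) C(320, c) C(64, v) / C(704, t). The exact (Freeman–Halton) p-value sums the tables no more probable than the one observed. Power comes from several thousand simulated trials per scenario. Ranges show the spread between repeated runs.

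**1. ZuraPrep doubles the rate of both controls**

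| Rates | Power, 320/320/64 | Power, areas pooled, 640/640/128 |
|---|---|---|
| 2% v 1% | 9–11% | 21–23% |
| 4% v 2% | 23–25% | 47–48% |
| 6% v 3% | 36–38% | 67% |
| 10% v 5% | 58–60% | 89–91% |
| 20% v 10% | 93% | over 99% |

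**2. Fixed excess for ZuraPrep, 320/320/64**

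| Background | +3 points | +5 points | +10 points |
|---|---|---|---|
| 0.5% | 71% | 97% | over 99% |
| 1% | 58% | 93% | over 99% |
| 2% | 46% | 83–85% | over 99% |
| 5% | 27% | 59% | 99% |
| 10% | 18% | 39% | 93% |
| 20% | 12% | 26% | 78% |
| 30% | 10% | 23% | 70% |

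**3. Grade.** Let a share *q* of sites score above zero under every product, and let ZuraPrep add 3% of sites scoring 2 or more. The signal compares *q* + (1 − *q*) × 0.03 with *q*. For *q* = 0.20 this is 0.20 + 0.80 × 0.03 = 22.4% v 20%, with power of 9–11%. For *q* = 0.10 (12.7% v 10%) it is 14–15%, and for *q* = 0.40 (41.8% v 40%) it is 6–7%. The same test on score 2 or more, at 3.2% v 0.2%, has 82–84%. If products differ only in grade, with equal rates of any reaction, the test rejects at its null rate, about 5% or less.

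**4. Both actives above vehicle, 320/320/64.** 5% v 1%: 11%; 10% v 5%: 16–17%; 20% v 10%: 41%; 10% v 2%: 54%; 15% v 5%: 56%.

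**5. What an interval would show.** The unpaired 95% half-width at a common rate *p* is 1.96 × √[p(1 − p)(1/n₁ + 1/n₂)].

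| Rate | ZuraPrep − ChloraPrep (320 v 320) | ZuraPrep − vehicle (320 v 64) |
|---|---|---|
| 2% | ±2.2 points | ±3.8 points |
| 5% | ±3.4 | ±5.9 |
| 10% | ±4.7 | ±8.1 |
| 20% | ±6.2 | ±10.7 |

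The 32 direct ZuraPrep–vehicle pairs alone, taken as independent, give 1.96 × √[(0.06 × 0.94 + 0.03 × 0.97)/32] = ±10.1 points at 6% v 3%. At 10% v 5% they give 1.96 × √[(0.10 × 0.90 + 0.05 × 0.95)/32] = ±12.8 points.

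**6. Pairing.** With a latent within-subject correlation of 0.5 to 0.8, Fisher's type I error falls to 2–3%, and its power for 25% v 20% falls from 27% to 19–22%. An exact McNemar test on the 288 ZuraPrep–ChloraPrep pairs gives 35–53% in the same cases.

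**The case against.** Three stronger readings are tempting, and the documents support none of them.

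- *The test would miss a relevant excess in most plausible cases.* The documents define neither an irritation rate nor a relevant excess, and the tables above go both ways. The 320/320/64 figures are also minimums for one area. Section 16.3 does not split the test by body area. Under Section 13.9 extra subjects are enrolled to cover test-day baseline failures, and those treated still count for safety.
- *The plan makes no use of severity.* That is true of the test only. Scores are tabulated, and score-3 reactions are listed as Adverse Events, attributed to a material, and lead to discontinuation.
- *A null result would be reported as no difference.* No section says so. The documents set no equivalence claim for irritation.

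The mild background in step 3 is an assumption too. Section 15.4 calls abrasion and adhesive reactions possible, not universal. Section 13.5 applies dressings only after the 10-minute sample, and subjects scoring 1 before baseline are excluded. With a background of 0.5–1%, an added 3 points is detected 58–71% of the time.

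It can also be said that an omnibus test followed by pairwise work is a conventional guard against multiplicity, and that Section 16.3 rests safety on Adverse Events, which makes Fisher's test supplementary. Both are fair. But that guard limits false positives, whereas the risk in a safety comparison is a missed excess, and estimating a difference needs no prior rejection. The Adverse Event route does not clearly cover score 2, since only score 3 is stated to qualify by itself. What stands of the objection limits the claimed size of the problem and leaves the gap in Section 16.3.

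**Conclusion.** The concern holds in a limited form. The omnibus Fisher test on any score above zero is the only planned inference on irritation. When it is not significant, the plan yields no between-product difference or interval, and grade enters no between-product inference at all. How much this costs depends on rates that the documents do not give. At the planned minimum in one body area, the test is weak for doublings of low rates, for small excesses of score 2 or more over a common mild background, and for many contrasts of both actives with the 64 vehicle sites. It is strong for 5 points over a background of 2% or less and for 10 points over 10% or less, and pooling the areas raises power throughout. These figures assume alpha 0.05 and, except in step 6, independent sites. The change is worth making because it is cheap and does not depend on which rates turn out to be true.

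**What to change.** In Section 16.3, remove the significance condition. Whatever the Fisher result:

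1. Report ZuraPrep minus ChloraPrep and ZuraPrep minus vehicle differences in irritation rate, with two-sided 95% confidence intervals, by body area.
2. Do this for any score above zero and for a worst post-application score of 2 or more.
3. Use a method that respects the within-subject pairing but draws on all treated sites, for example a marginal risk difference with subject as the cluster, with a named fallback for sparse counts. The vehicle contrast should not rest on the 32 direct pairs alone.
4. State the unit and alpha of the Fisher test, and that a non-significant result is not evidence of no difference.

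The amendment of 08/29/2017 was issued after testing was complete, so an analysis added at or after that point should be labelled as post-testing.

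The scores are already collected, so the cost is protocol wording and a few table rows. The downside is a few more descriptive comparisons, and intervals against vehicle that will be wide and may not exclude a modest excess.
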